### 7.1.2.3 Subject Population(s) for Analysis

Statistically evaluable subjects are those who have attended at least 50% of the available yoga sessions offered on the days they receive radiation treatment.

	Subject attends treatment	Subject misses treatment (inclement weather or machine downtime)
Yoga offered	Counts towards evaluability	Counts towards evaluability
Yoga session not offered	Doesn't count for or against evaluability	Doesn't count for or against evaluability

- All caregivers will follow the same evaluability guidelines as the radiation therapy population. If their associated subject undergoes treatment, the caregiver is also considered to have undergone “treatment”.

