### No Yoga Treatment Arm

Control patients who are randomized to standard of care will not undergo any yoga intervention or participate in any structured yoga program during the study duration. They will undergo cancer and side effect treatment per standard of care, and they will be asked to complete all study-related questionnaires at the same time points as the patients in the yoga treatment arm.

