#### **7.1.2 Randomized phase II trial**

##### **7.1.2.1 Sample size determination**

Our goal is to estimate effect sizes for a larger study. We are setting our recruitment aim for phase 2 up to 48 subjects, a 20% increase from our target enrollment in order to account for potential subject drop out and arrive at N = 40. Inclusion of subject data from

the feasibility portion results in  $N = 55$  up to  $N = 63$  should subject attrition levels prove lower than expected. Two groups (35 v 20) give us power to estimate an effect size for yoga participation with a 95% confidence interval that is approximately 1.1 standard-deviations wide (compared to the SD of the raw measure). For the corresponding caregivers, two groups (20 v 20) give power to estimate a CI that is 1.3 SD wide. The effect will be measured as a time x treatment interaction (difference of difference scores). From our own preliminary data, and from Hwang et al. (2008), we know that the within subject correlation for fatigue measures is approximately 0.5, and that the SD for the difference score will be similar to that of the raw measure at individual time points. For the time x treatment interaction, we will be able to detect a standardized effect size of  $d=0.7$  (0.8 for caregivers) at  $\alpha=0.05$  (one-sided) with 80% power.

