#### **7.1.2.2 Statistical Methods**

This randomized study is a two-arm longitudinal controlled trial of yoga as a means of reducing fatigue over the course of radiation therapy for prostate cancer, with measures taken prior to treatment, during treatment, and in follow-up. The analysis will include the initial subjects from the feasibility study as an addition to the treatment arm, and we will control for any differences between the feasibility group and the randomized treatment arm using indicators. The primary measure, and most secondary measures, are Likert-style summary scores on a 0-10 scale and will be treated as Gaussian. The exception is retention, which is a binomial count of those remaining enrolled to the end.

Prior to performing analyses, standard data cleaning procedures will be applied (e.g., checking for outliers and data entry errors, creating summary scores for analysis, and checking that analysis assumptions are met). The assumptions underlying the statistical methods will be examined through the use of standard tests of normality, and graphical displays (27). All analyses will be conducted using Stata software (Stata Corporation, College Station, TX).

We will calculate descriptive statistics for all variables in the study. For outcome variables, we will summarize by treatment group (Yoga versus control) and by time point. We will also estimate correlations within subject for each of the study measures taken at different times.

The primary outcome for the randomized, phase II study will be the difference score of BFI fatigue while undergoing radiation therapy minus BFI fatigue prior to radiation. The primary hypothesis will be tested using a two-group t-test to compare difference scores between Yoga and control groups. This will be a one-sided test with type-1 error at  $\alpha=0.05$ . Similar analysis will be conducted using BFI fatigue at follow-up versus pre-radiation, and for all of the FACT-G fatigue measures. We will test the difference using a one-sided z-test. The FACT-G analysis will be repeated for caregivers (Aim 4).

Effect sizes will be reported for all outcome measures as standardized differences. The effect size will reflect the time x treatment interaction, and the standard deviations will be adjusted for within-subject correlation to aid in designing a larger study.

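### The only phase II analysis population is defined by yoga attendance, and the plan does not say whether the primary yoga-control test uses it; if it does, low attenders are dropped from the yoga arm only

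*Combined protocol and SAP*

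**What the plan says.** Section 7.1.2.3, inside the randomised phase II plan, defines one population: "Statistically evaluable subjects are those who have attended at least 50% of the available yoga sessions offered on the days they receive radiation treatment". The list of evaluable bands after it starts at 50% attendance and has no place for a control. Caregivers are tied to the same rule: "All caregivers will follow the same evaluability guidelines as the radiation therapy population".

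Under Section 6 (No Yoga Treatment Arm), control patients "will not undergo any yoga intervention or participate in any structured yoga program during the study duration", but "they will be asked to complete all study-related questionnaires at the same time points as the patients in the yoga treatment arm". Section 7.1.2.1 counts 20 controls against 35 yoga patients (20 randomised plus 15 from the feasibility stage), and 20 v 20 caregivers.

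For the primary analysis, Section 7.1.2.2 says: "The primary hypothesis will be tested using a two-group t-test to compare difference scores between Yoga and control groups". It names no analysis set. It adds the feasibility patients to the yoga arm and says that differences between them and the randomised yoga patients will be controlled with indicators. No as-assigned, intention-to-treat or per-protocol set is defined anywhere.

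**The concern.** Two analysts could follow this plan and test different groups. One would compare everyone retained, by arm. The other would compare yoga patients with at least 50% attendance against all controls. For randomised patients, the second approach excludes on something that happens after randomisation and can happen in one arm only. If men who feel worse come to fewer classes, the filter flatters yoga; if men who feel well skip classes, it works against yoga; if attendance is unrelated to fatigue, there is no bias.

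The stated aim is an effect size with which to design a larger trial. That number, and the error rate of the one-sided test, depend on a choice that the plan leaves open.

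**Working it through.** **1. The plan's own figures.** Inputs from 7.1.2.1: 35 v 20 patients, 20 v 20 caregivers, one-sided 5%, 80% power. The unit is 1 SD, because the plan expects that "the SD for the difference score will be similar to that of the raw measure at individual time points".

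- Patients: √(1/35 + 1/20) = 0.280. The 95% CI width is 2 × t(0.975, 53) × 0.280 = 1.12 SD (plan: about 1.1). Detectable d = (1.645 + 0.842) × 0.280 = 0.70 (plan: 0.7). Noncentral-t power at d = 0.7 is 79.4%.
- Caregivers: √(1/20 + 1/20) = 0.316. Width 1.28 SD (plan: 1.3). Detectable d = 0.79 (plan: 0.8). Power at d = 0.8 is 79.9%.

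The planned figures reproduce.

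**2. Which set does the text point to?**

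- For the attendance set: the title of 7.1.2.3; the bands starting at 50%; the description in 7.1.2.1 of the target as the effect of yoga participation; and the counting of accrual in evaluable patients in 3.3.1 and 7.1.1.
- Against it: 7.1.2.2 summarises outcomes by treatment group and does not restrict the test to evaluable subjects. The sample size in 7.1.2.1 allows for attrition only, giving a larger N "should subject attrition levels prove lower than expected", with nothing for low attendance.

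The text does not decide the matter.

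**3. Bias if the attendance rule governs.** Let q be the share of randomised yoga patients below 50% attendance and ρ the correlation of attendance with a smaller BFI rise. Neither is in the documents; both are assumed. With normal scores, bias = ρ × φ(z_q)/(1 − q), positive favouring yoga.

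- q = 20%: 0.280/0.8 = 0.350, so ±0.07 SD at ρ = ±0.2 and ±0.14 SD at ρ = ±0.4.
- q = 40%: 0.386/0.6 = 0.644, so ±0.13 and ±0.26 SD.

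At the BFI SD of 2.8 in Section 3.2, 0.14 SD is 0.39 points and 0.26 SD is 0.72 points.

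**4. Type I error.** I simulated 200,000 trials per cell with unit-SD change scores and no yoga effect. Yoga patients below the threshold were removed and all 20 controls kept. The 15 feasibility patients were taken as already above 50%, an inference from their being called evaluable in 7.1.1. Approximate one-sided error at nominal 5%:

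| Excluded | ρ | Bias (SD) | Pooled 35 v 20 t-test | With feasibility indicator |
|---|---|---|---|---|
| 20% | -0.4 | -0.14 | 1.7% | 2.0% |
| 20% | -0.2 | -0.07 | 3.0% | 3.2% |
| 20% | 0 | 0 | 5% | 5% |
| 20% | 0.2 | 0.07 | 8% | 7.5% |
| 20% | 0.4 | 0.14 | 12.6% | 11% |
| 40% | -0.4 | -0.26 | 0.6% | 0.9% |
| 40% | 0 | 0 | 5% | 5% |
| 40% | 0.4 | 0.26 | 22% | 17% |

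In the last column the yoga-control contrast rests on the randomised patients. If the feasibility patients are not selected on attendance, the pooled ranges narrow to 2.9–8.1% (20% excluded) and 2.1–10.3% (40% excluded). For caregivers at 20 v 20, the ranges are 2.0–10.7% and 0.9–16.8%.

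**5. Scale.** The planned CI half-width is 1.12/2 = 0.56 SD. A bias of 0.07 SD is one-eighth of it, 0.14 SD one-quarter, and 0.26 SD just under half.

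**6. The rule's wording.** The sentence in 7.1.2.3 counts sessions on days when radiation is received; its table also counts sessions offered on missed-treatment days. As an illustration, suppose 16 sessions are offered, 2 of them on missed days. A man attending 7 of the other 14 is at 50% by the sentence. He is at 7/16 = 44% by the table, if those 2 enter the denominator.

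**The case against.** The strongest defence is that a rule about attending offered sessions concerns those who were offered them. A reader might infer that no control is evaluable and that the primary test cannot be run. The documents do not support that: 7.1.2.1 counts 20 controls and Section 6 collects their questionnaires. This part of the defence stands.

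An attendance-based estimate may also be a deliberate choice in a phase II study meant to estimate effect sizes, and the wording about yoga participation and evaluable accrual fits that. But 7.1.2.2 does not say so, and such an estimate still would not compare the assigned groups.

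The maximum N of 63 (48 + 15) might be read as counting everyone enrolled, which would settle the matter against the attendance set. It does not, because 7.1.1 calls the 15 evaluable.

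On size, the defence is largely right. The excluded shares and correlations are assumptions; 40% is extreme, since the only loss figure in the documents is up to 20% dropout (4.5.1). The feasibility indicator, if it enters the primary model, reduces the distortion. Low attenders may largely be the dropouts already allowed for, so a further loss of precision beyond that allowance is not shown.

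**Conclusion.** The point holds as a gap in specification with a possible bias attached. The one phase II population that the plan defines depends on yoga attendance, and the plan does not say whether the primary test uses it. If it does, exclusion falls on the yoga arm alone: after randomisation for the 20 randomised yoga patients, and as a selection rule for the 15 feasibility patients, who were never randomised. Caregivers are in the same position, taking control caregivers to be offered no yoga either.

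The gap itself needs no assumption; the size does. The 20% rows of the table are the ones to carry forward, and the 22% cell should not be the headline. A reader might infer that the filter favours yoga. The documents give no link between attendance and fatigue, so either sign, or no bias, is possible. The planned power and interval widths are not in error.

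The matter bears on the primary comparison and should be settled before outcomes are compared by arm. The two readings of the attendance rule are a minor clarification.

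**What to change.** In 7.1.2.3:

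1. State that the primary phase II comparison uses all randomised patients with BFI data, and all randomised caregivers with FACT-G data, in their assigned arm regardless of attendance. If feasibility patients are added to yoga, include all of them regardless of attendance, with the indicator from 7.1.2.2. Report missing data by arm, because a set defined by available data is still open to unequal loss. Continue the scheduled questionnaires, where the subject agrees, in those who stop yoga.
2. Keep the 50% rule and the attendance bands for feasibility and for a secondary analysis labelled per-protocol.
3. Reconcile the sentence with the table on missed-treatment days, and say whether the word evaluable in 3.3.1 and 7.1.1 carries this meaning.

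**Cost.** Mostly wording, plus some follow-up questionnaires: 4.5.2 provides only for contact about reasons for withdrawal. Section 4.5.1 allows withdrawal for not following instructions without saying whether missed classes count, which affects how many people this concerns. Taking in every feasibility patient may bring the yoga group above 35.

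Power at d = 0.7 is about 79% pooled at 35 v 20, or about 70% if the contrast rests on 20 v 20 randomised patients. Dilution is possible: if 20% of yoga patients gain nothing (assumption), d = 0.8 × 0.7 = 0.56 and pooled power is about 63%. For caregivers, d = 0.8 × 0.8 = 0.64 likewise gives about 63%.

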### Study Summary

Title	A Feasibility Study Followed by a Randomized Phase 2 Study of Yoga for Radiation Therapy Side Effects in Prostate Cancer
Short Title	Yoga for Prostate Cancer
Protocol Number	UPCC# 05813
Phase	Feasibility study followed by a randomized Phase II study
Methodology	A single arm pilot followed by a 2-arm study
Study Duration	12 months for Feasibility. 36 months for Phase II
Study Center(s)	Perelman Center for Advanced Medicine
Objectives	The purpose of this study is to ascertain the feasibility of yoga interventions as well as the effect of yoga on radiation-related fatigue, sexual dysfunction and urinary incontinence in patients with non-metastatic prostate cancer.
Number of Subjects	63
Diagnosis and Main Inclusion Criteria	Non-metastatic prostate cancer patients undergoing radiation therapy
Study Product, Dose, Route, Regimen	N/A
Duration of administration	Twice weekly yoga sessions for duration of radiation treatment.
Reference therapy	N/A
Statistical Methodology	The primary hypothesis will be tested using a two-group t-test to compare difference scores between Yoga and control groups.

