5. The International Prostate Symptom Score Sheet (IPSS) will be used to determine the severity of enlarged prostate conditions and measures UI symptoms. Scores on this scale range from 0 to 35, where a score of 8-19 indicate moderately symptomatic, and 20-35 – severely symptomatic. The 8th question on this scale is on QOL and is assigned a score of 1 to 6, where 6 indicates terrible. The IPSS will be completed by patients at the following time points:
- a. Prior to start of radiotherapy i.e. on the day of consultation or on the day of simulation or setup.
  - b. In the 4th week of radiotherapy (when treatment-related symptoms are expected to peak)
    - i. A treatment week is defined as 5 consecutive days of radiotherapy. If a patient misses treatment for any reason his treatment week is shifted back one day.
  - c. Within a week of the last yoga class or by the end of radiation.
6. Yoga interventions will consist of twice-weekly classes, 75 minutes each that will be offered by a yoga instructor. The simplified poses to be used in this study will

include seated (using a chair), standing, and reclining. Yoga poses can and will be modified based on each subjects specific needs and restrictions. Not all yoga poses will be performed each session. Each session will begin with breathing and centering techniques (taking inventory of the levels of energy, posture, stress, emotions, and breath). Yoga poses will consist of the following:

- Sitting on chair: neck and shoulder series (neck and shoulders side, front and back movements, shoulder rolls, and arms movement), table pose with opposite arm and leg movement, side bend (seated Parighasana), simple chair twist (Bharadvajasana).
- Standing poses: mountain pose (Tadasana Samasthithi), warrior II series (Virabhadrasana II), half moon (Ardha Chandrasana) variation at the wall, front warrior series, forward stretch/ bend variation (Uttanasana).
- Recline poses will include: inverted lake pose (Viparita Karani), bridge pose variation (Setubandha Sarvangasana), recline/ sided bound angle pose (Supta Baddhakonasana), camel pose (Ustrasana) at the wall, modified shoulder stand (salamba sarvangasana), reclining big toe posture with a belt (Supta Padangustasana), and corpse pose (Savasana).

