## **6 Study Procedures**

### Feasibility and Yoga Treatment Arm

Subjects will participate in two 75 minute sessions per week for the duration of radiation treatment with a yoga instructor offered for free by Patient Family Services in the Perelman Center of Advanced Medicine. Numerous sessions will be offered each week. Each session will begin with breathing and centering techniques (taking inventory of the levels of energy, posture, stress level, emotions, and breath). Yoga poses will consist of the following and can be modified based on patient needs: Sitting on chair: neck and shoulder series (neck and shoulders side, front and back movements, shoulder rolls, and arms movement), Table pose with opposite arm and leg movement. Side bent. Simple chair twist. Standing poses: Mountain pose, Warrior II series, Half Moon variation at the wall, Front warrior series, forward stretch/ bend variation with a chair. Recline poses will include: inverted lake pose (legs up the wall with a blanket for support), bridge pose variation, recline/ sided bound angle pose, modified Camel pose at the wall, modified Shoulder stand (legs up the wall with block support), reclining big toe posture with a belt, and corpse pose (Savasana – final rest). Modifications can and will be made based on

each subjects specific needs and physical restrictions. Poses will be added progressively. Not all poses will be done each session. Additionally subjects will fill out 4 types of QOL forms at various points during the study. The first is to be completed prior to start of radiation treatment, bi-weekly during treatment and within a week of the last yoga class or by the end of radiation

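### The definition of 'evaluable' divides by yoga sessions offered rather than sessions asked for, so the 15-of-75 feasibility count depends on how many classes are offered

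*Combined protocol and SAP*

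**What the plan says.** Section 3.1 makes phase 2 conditional on feasibility. Sections 3.3.1 and 7.1.1 measure feasibility as a count: at least 15 evaluable patients among the first 75 approached. Neither section says what evaluable means. The only definition is in section 7.1.2.3, under the randomized phase II heading: a subject is evaluable who has "attended at least 50% of the available yoga sessions offered on the days they receive radiation treatment".

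A small table follows that sentence. For a session offered on a day when radiation is given, the entry is "Counts towards evaluability". The entry is the same for a session offered on a day when radiation is missed because of weather or machine downtime. Sessions not offered do not "count for or against evaluability". A list of attendance bands comes next, the highest being above 80%.

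The number of sessions is described in three places. The Study Summary has "Twice weekly yoga sessions for duration of radiation treatment". Section 3.2, item 6, has "twice-weekly classes, 75 minutes each that will be offered by a yoga instructor". Section 6 has subjects taking part in two 75-minute sessions a week and adds: "Numerous sessions will be offered each week". The plan does not state the number of classes offered per week or the length of the radiation course.

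**The concern.** The rule measures a man against what the centre puts on, not against what the protocol asks of him. If the timetable has more than two classes a week on radiation days, so that men can choose a convenient slot, each extra class enlarges the denominator and lowers the score of a man who does what he was asked. The feasibility threshold is a fixed count, so moving one man across the 50% line can turn a go into a no-go. The decision could then reflect the timetable rather than the men's willingness to attend.

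There is a smaller problem in the same place. The sentence counts only sessions on days when radiation is received. The table also counts sessions on days lost to weather or machine downtime. Two analysts, one using the sentence and one the table, could class the same man differently.

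**Working it through.** **The plan's own figure.** 15/75 = 20.0%. It is a fixed count with no stated error rates, so there is nothing further to reproduce. One man fewer gives 14/75 = 18.7%, a no-go.

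**Inputs from the plan.** Threshold 50% (section 7.1.2.3); two sessions a week asked for (section 6).

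**Assumed, because the plan gives no figure.** k = 2 to 5 sessions offered per week on radiation days; a course of W = 8 weeks, with 6 and 9 as a range; a chance p of attending each session, independent between sessions.

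**1. A man who attends exactly the two asked for.** Score = 2W/(kW) = 2/k.

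| k | 2 | 3 | 4 | 5 |
|---|---|---|---|---|
| Score | 100% | 67% | 50% | 40% |

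He falls below 50% only at k = 5 or more. From k = 3 his best score is 67%, so without extra sessions he cannot reach the band above 80%.

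**2. A man who attends some of his two a week.** With W = 8 he is asked for 16 sessions and attends X of them, X ~ Binomial(16, p). The rule requires X ≥ kW/2 = 4k, that is 8, 12 or 16 for k = 2, 3 or 4.

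| p | k = 2: P(X ≥ 8) | k = 3: P(X ≥ 12) | k = 4: P(X = 16) |
|---|---|---|---|
| 0.6 | 0.86 | 0.17 | 0.0003 |
| 0.7 | 0.97 | 0.45 | 0.003 |
| 0.8 | 0.998 | 0.80 | 0.03 |

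The last column is p^16; for example, 0.7^16 = 0.0033. Other course lengths at p = 0.7:
- 6 weeks (6, 9 or 12 needed of 12): 0.96, 0.49, 0.014.
- 9 weeks (9, 14 or 18 needed of 18): 0.98, 0.33, 0.002.

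The pattern does not depend on the assumed course length.

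**3. Sentence against table.** The table's entry is taken in its natural sense: the session enters the denominator, and the numerator if attended. Suppose 16 sessions are offered, 2 of them on days lost to weather or downtime.
- Man A attends 7, all on radiation days. Sentence: 7/14 = 50.0%, evaluable. Table: 7/16 = 43.8%, not evaluable.
- Man B attends 8, 2 of them on missed days. Sentence: 6/14 = 42.9%, not evaluable. Table: 8/16 = 50.0%, evaluable.

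These are the only two patterns that change class in this example. Chance = P(7 of 14)(1−p)² + P(6 of 14)p². At p = 0.7 this is 0.0618 × 0.09 + 0.0232 × 0.49 = 0.017. At p = 0.6 it is 5.8%, and at p = 0.8 it is 0.2%.

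If instead there are 16 radiation-day sessions and one more on a missed day, a man changes class only if he attends exactly 8 of the 16 and not the extra one (8/16 = 50% against 8/17 = 47%). The chance is P(8 of 16)(1−p):
- p = 0.6: 0.142 × 0.4 = 5.7%.
- p = 0.7: 0.049 × 0.3 = 1.5%.
- p = 0.8: 0.0055 × 0.2 = 0.1%.

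**The case against.** The strongest reply is that only two sessions a week are on offer. The Study Summary and section 3.2 can be read that way, and the remark in section 6 may mean no more than a choice of time slots for the two required. The attendance bands fit this reading, since the top band would otherwise be closed to a man who attends exactly as asked. This may be what was intended, and if so the denominator problem vanishes. But section 7.1.2.3 counts sessions that are available and offered, with no cap at two, and under the slots reading every slot is still an offered session. The intended rule and the written rule then differ.

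A reader might go further and infer that the rule fails fully adherent men. That needs five or more sessions a week on radiation days, which the plan does not establish.

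On missed days, the sentence can be taken as the general rule and the table as adding two named reasons, with other reasons falling back to the sentence. That is a sensible reading, but the sentence and table still give different counts. Two stronger readings are tempting and do not hold:
- That the table's entry might add to the numerator only. The same words in the neighbouring cell plainly mean that the session enters the calculation in the ordinary way.
- That missed-day sessions always come on top of a full course, because "If a patient misses treatment for any reason his treatment week is shifted back one day". That text in section 3.2 fixes the timing of the fourth-week questionnaires and says nothing about counting yoga sessions.

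Finally, section 7.1.2.3 belongs to phase II, and the pilot's stated aim is recruiting and retaining men. The link to the feasibility count is therefore an inference. It is the reasonable one, because without it the pilot's endpoint has no definition.

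**Conclusion.** The point stands, mainly for the denominator. Read literally, the rule makes evaluability depend on an unstated number of classes. At three a week on radiation days, a man attending 70% of what he was asked has a chance of 0.45 of being evaluable, against 0.97 at two a week; at four a week he has almost none. These figures rest on an 8-week course, independent sessions and no extra sessions attended. If two sessions a week are offered, there is no effect.

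The mismatch over missed days is real but minor. In the examples worked it reclassifies under 6% of men at attendance 0.6 and under 2% at 0.7, all of them within about one session of 50%. A reader might infer that it alone could swing the go/no-go decision. The documents give no enrolment, attendance or missed-day figures to support that.

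The point concerns the feasibility count and makes no claim about the phase II t-test. It should be settled before the count is made, so that the rule cannot be chosen with the result known.

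**What to change.** 1. Reconcile section 3.2 (item 6), section 6 and section 7.1.2.3 on how many sessions are offered and how many are asked for.
2. Define attendance as sessions attended divided by sessions the protocol asks the man to attend, reduced in weeks when fewer are offered and capped at 100%. The table's row for sessions not offered then still holds.
3. Make the sentence match the table for days lost to weather or machine downtime: a session asked for on such a day is in the denominator, and in the numerator if attended. Say that days missed for other reasons follow the sentence and are left out.
4. State in sections 3.3.1 and 7.1.1 that evaluable has this meaning, fixed before the feasibility count.

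This changes the measurement rule only. The yoga schedule stays as it is, and no patients or visits are added. The cost is a rewritten definition and a weekly log of sessions offered and attended, which any version of the rule needs and which the plan does not describe.
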